
D2. Study Population & Eligibility Criteria

The study will be based at the ambulatory obstetrical practices of Baystate Medical Center, a large tertiary care facility in Western Massachusetts that serves a socioeconomically diverse population; 4,300 infants are delivered annually, 57% are Hispanic (predominantly from Puerto Rico with ~58% having income <\$15,000 per year). Eligible women will be Hispanic, overweight or obese (BMI >25 kg/m²), and 16-45 years of age. We will exclude women with 1) prepregnancy BMI <25 kg/m², 2) history of type 2 diabetes, heart disease, or chronic renal disease, 2) contraindications to participation in moderate physical activity or to a low-fat/high-fiber diet (e.g., Crohn's disease, ulcerative colitis), 3) inability to read English or Spanish at a 6th grade level, 4) <16 or >45 yrs of age, 5) >20 wks gestation, 6) current medications which adversely influence glucose tolerance, 7) not planning to continue to term or deliver at the study site, or 8) pregnant with twins or triplets. Women who have a very early preterm birth (<34 wks), a miscarriage, or a still birth after enrollment or a stillbirth will be excluded. Women who become pregnant again in the year following delivery will be censored at the time of their positive pregnancy test.

D3. Recruitment, Baseline Assessment, and Sample Size

Bilingual (Spanish and English) and bicultural health educators will recruit women at the first prenatal care visit (~10 wks gestation). Women will be informed of the aims/procedures of the project, sign an informed

consent, and complete a screening form to determine eligibility. The baseline assessment will be collected via standardized questionnaire and the pregnancy blood sample will be taken (see Figure 1). Expectations for the study and a contacts schedule (face-to-face meeting, mailings, booster telephone calls) will be reviewed. Each assessment and interview completed is associated with a gift card for a total of up to \$360, to be handed out after completing the study component.

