- 2) the postpartum face-to-face meeting takes place at the routine 6 wk postpartum visit and adherence is facilitated by bus passes, cafeteria vouchers, and the 2006 Mass insurance reform law providing free health care insurance for residents earning <150% of the federal poverty level. However, if a woman does not intend to attend this visit, the health educator will meet the women at locations outside the hospital, with consideration for the participant's and the health educator or assessors level of comfort (i.e., their pediatrician's office, their home, a community center). Locations will be selected for privacy (for example, an unused exam room at a pediatrician's office) and only staff who have experience making home visits will be permitted to complete home visits.
- 3) The 6 mos and 1 yr postpartum assessments will be conducted in the hospital or at a location outside the hospital with consideration for the participant's and the health educator or assessors level of comfort
- 4) Approximately 5% of participants in our prior pregnancy cohorts left the Springfield area after delivery; however, travel funds are budgeted for assessors to travel to the broader tri-state area (MA, NY, CT) if necessary.
- 5) Delivering the intervention does not rely upon women remaining in the immediate area during the postpartum year as it is based upon tested mailed print-based materials and telephone contacts. In addition to providing home/cell/work numbers, women will be asked to provide the contact information for a person close to them. Pre-paid cell phone time will be provided as an additional incentive.

D.5. Randomization

Immediately prior to randomization (~12 weeks GA), participants will be evaluated for study inclusion by answering if their provider has restricted their physical activity during this pregnancy. If they answer yes, their medical records will be reviewed by [name] (Co-Investigator, and Director of Maternal/Fetal Medicine at Baystate). Eligible patients will be randomized into either the Lifestyle Intervention vs. the Health and Wellness Comparison Group. Randomization will be stratified based on age (<30, >30 years) and pre-pregnancy BMI (overweight >25-<30 kg/m² vs. obese >30 kg/m²). Within each strata, a blocked randomization will be used such that both treatment groups will be assigned an equal number of times in each set of 4 sequentially enrolled patients.

D.6. Intervention

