Cord insulin (μ U/ml)	288	4.7	1.6
Cord adiponectin (μ g/ml)	288	9.7	3.2
Cord leptin (ng/ml)	288	13.6	4.5
Birthweight-for-gestational age z-score [fetal growth]	288	0.93	0.3
Birthweight (g)	288	640	212
Ponderal Index (g/cm ³)	288	0.3	0.1
Birthweight-for-length z-score (WFL-z)	288	0.77	0.3
Head circumference (cm)	288	1.1	0.4
Aim #4: Offspring Outcomes at 1yr			
Adiponectin (μ g/ml)	264	5.8	2
Leptin (ng/ml)	264	1.8	0.6
Weight-for-age z score (WFA-z)	264	0.98	0.3
Length-for-age z score (LFA-z)	264	0.94	0.3
Sum of skinfolds (mm)	264	4.2	1.5
Ratio of skinfolds	264	0.16	0.1
Waist circumference (cm)	264	2	0.7

D.18. Environment

In brief, Baystate Medical Center, the recruitment site, is the major medical resource in Western Massachusetts and the third largest acute-care hospital in New England, with 725 beds currently in service and approximately 4,500 deliveries per year. The School of Public Health and Health Sciences at UMASS maintains a micro computer research room for faculty, staff and students. Fifteen PC compatible microcomputers, a file server, a scanner and two laser printers are connected to the Department's Local Area Network (LAN). The LAN enables secure hard disk space for research projects that is accessible by multiple users and backed-up daily. [name] (Department of Laboratory Medicine, Harvard University) lab at Children's Hospital, Boston, MA is a fully equipped laboratory with all of the requisite centrifuges, water baths, pipetters, etc. required to do the hormonal assays.

D.19. Timeline

This is a 5 year study. The timeline allows 12 months for study start up and protocol development, 24 months of recruitment, and follow-up of the last remaining participant (an additional 18 months from last enrollment). Data analysis will be ongoing and the last 6 months of the study will be dedicated to final analyses and manuscript writing.

D.20. Limitations and Alternatives

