At the time of recruitment (~10 weeks gestation), a blood sample to evaluate serum biomarkers associated with insulin resistance and other cardiovascular risk factors will be collected (termed "blood draw"). A total 700 microliters (uL) of serum will be collected which is equivalent to 1.5 milliliters (mL) or less than a teaspoon of whole blood. Physical activity, diet, and other covariates will also be assessed at recruitment. Subsequent assessments will be conducted at ~24-28 weeks gestation, after 32 weeks gestation, 6-weeks postpartum, ~6.5-months, and ~13-months postpartum. A urine pregnancy test will also be performed at the postpartum assessments. Women who are identified as having a positive pregnancy test will be removed from the study at the time of their positive pregnancy test and referred to their obstetric care provider. Measurements of compliance with exercise and diet will include activity monitors (worn for a 4-day period within each of these assessment time points), tracking the number of intervention sessions attended, number of booster calls participated in, number of assessments (e.g., questionnaires, blood samples) completed, as well as an assessment of degree of participation in physical activity and healthy dietary behaviors. No participants will be excluded from the study based on noncompliance. Assessments to measure other important covariates will also be collected at these assessment time points. Subjects will be under no obligation to complete the assessments, activity monitoring, or blood collections. Pregnancy and postpartum medical and laboratory records will be reviewed for obstetric and medical history, clinical characteristics of the index pregnancy, and laboratory results. All data will be used specifically for research purposes.

Potential Risks:

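### The 18 months of follow-up after last enrolment in D.19 is about 1 to 2 months short of the last woman's 1-year visit on the protocol's own nominal dates

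*Combined protocol and SAP*

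**What the plan says.** D.19 opens with "This is a 5 year study". It then divides the period: "The timeline allows 12 months for study start up and protocol development, 24 months of recruitment", followed by "follow-up of the last remaining participant (an additional 18 months from last enrollment", and finally "the last 6 months of the study will be dedicated to final analyses and manuscript writing". It adds that data analysis will be ongoing throughout.

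Other sections fix the dates that the follow-up block has to cover:

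- **Entry.** D3 says health educators "will recruit women at the first prenatal care visit (~10 wks gestation". Section E.1 (Sources of Materials) takes the first blood sample "At the time of recruitment (~10 weeks gestation". D.5 places the eligibility check "Immediately prior to randomization (~12 weeks GA". D2 excludes women beyond 20 weeks.
- **Delivery.** No week is given. D2 requires only that women plan to continue to term.
- **Last visit.** D1 has follow-up continuing for one year postpartum, and D.12.1 and D.12.2 also name 1 year. Section E.1 lists the postpartum assessments as "6-weeks postpartum, ~6.5-months, and ~13-months postpartum".
- **Planned numbers.** D.17 expects to recruit 333 women over 24 months and to have 264 women and children at 1 year.

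**The concern.** The 18 months must contain the rest of the last woman's pregnancy plus at least a year postpartum. From about 10 weeks' gestation, the pregnancy alone takes nearly 7 months, so 18 months does not reach even the 12-month visit, and falls further short of the 13-month visit in Section E.1. The four blocks of the timeline use up the five years exactly, with no stated slack. Nothing in the plan stops enrolment of early-gestation women near the end of recruitment, and nothing says that late visits may run into the analysis period.

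The outcomes at stake are those that depend on the 1-year visit: the postpartum rows of Table 3 and the 1-year offspring rows of Table 4, all powered on 264. That visit also produces fasting samples from mother and child, 4-day actigraphy and diet recalls. All of these need processing before analysis, and D.12.1 has samples shipped only periodically to the assaying laboratory.

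**Working it through.** **1. The plan's own total.** 12 + 24 + 18 + 6 = 60 months, which agrees with the stated five years. The sum is right; the question is the 18.

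**2. Months needed after entry.** Inputs: entry at about 10 weeks (D3, E.1) or 12 weeks (D.5); last visit at 12 months (D1) or about 13 months (E.1); delivery at 40 weeks, which is an assumption, with 37 to 41 weeks as the range. One month is 30.44 days, or 4.348 weeks.

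Months needed = (delivery week − entry week) / 4.348 + months postpartum at the last visit.

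For entry at 10 weeks and delivery at 40: 30 / 4.348 = 6.9 months. The 12-month visit falls at 6.9 + 12 = 18.9 months and the 13-month visit at 6.9 + 13 = 19.9 months. Against 18, the shortfall is 0.9 or 1.9 months.

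**3. Sensitivity.** Shortfall in months; a negative value means the visit fits.

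| Entry week | Delivery week | 12-month visit | 13-month visit |
|---|---|---|---|
| 10 | 37 | 0.2 | 1.2 |
| 10 | 40 | 0.9 | 1.9 |
| 10 | 41 | 1.1 | 2.1 |
| 12 | 37 | −0.25 | 0.75 |
| 12 | 40 | 0.4 | 1.4 |
| 16 | 40 | −0.5 | 0.5 |
| 20 | 40 | −1.4 | −0.4 |

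The break-even entry week with delivery at 40 weeks is 40 − 6 × 4.348 = 13.9 weeks for the 12-month visit and 40 − 5 × 4.348 = 18.3 weeks for the 13-month visit.

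**4. Women affected if follow-up stopped at 18 months.** Assume uniform accrual, every woman entering at 10 weeks, delivery at 40 weeks and the attrition projected in D.17.

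- Accrual: 333 / 24 = 13.9 women per month.
- Enrolled women affected: 13.875 × 0.9 = 12.5 and 13.875 × 1.9 = 26.4.
- Scaled to the 1-year cohort by 264/333: 9.9 and 20.9, or about 10 to 21 of 264 (4 to 8%), leaving 254 to 243.

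**5. Effect on power.** Detectable differences scale with 1/√N: √(264/254) = 1.02 and √(264/243) = 1.04. The Table 3 value for postpartum weight loss would move from 2.1 to at most 2.1 × 1.04 = 2.2 kg.

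**6. Position in the calendar.** Recruitment ends at month 12 + 24 = 36 and the 18-month block at month 54. The last visit falls at 36 + 18.9 = 54.9 or 36 + 19.9 = 55.9, which leaves 5.1 or 4.1 of the 60 months.

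**The case against.** The strongest reply is that 18 months is a parenthetical planning figure attached to a commitment to follow the last participant, and that D1 separately commits to a year postpartum. No section sets a data cutoff or a database lock at month 54. Analysis is ongoing, and an overrun of 1 to 2 months fits inside the final 6. This stands. A reader might infer that the last enrollees will have no 1-year assessment and that the 1-year sample must fall below 264; the documents do not say so. They also do not say that visits may run past the block, and that is the gap to close.

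A reader might also infer that every postpartum and child outcome is affected. That is not supported. The 6-week and 6-month maternal and child measures (D.12.1 to D.12.3) and the delivery outcomes in Table 4 (N = 288) fall well inside 18 months. For repeated outcomes, the mixed model in D.16 still uses a woman's earlier visits.

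The size is also open to challenge. The 40-week delivery is assumed, entry is allowed up to 20 weeks, and the upper end of the shortfall rests on the 13-month date in Section E.1 while other sections say 1 year. The count of 10 to 21 is therefore near an upper bound. The mismatch itself does not disappear: the 13-month visit misses by 0.75 months even when counted from randomisation at 12 weeks with delivery at 37. The 12-month visit does fit in that case.

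**Conclusion.** The 18-month figure is wrong as written. On nominal dates and with delivery assumed at 40 weeks, the last participant needs about 19 to 20 months. The range, over the two visit dates, is 0.2 to 2.1 months short for entry at 10 weeks with delivery between 37 and 41 weeks. Only entry well after the stated norm of about 10 weeks closes the gap at a 40-week delivery.

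The consequence is modest and conditional. Only the 1-year outcomes could be touched, only if follow-up were actually cut at 18 months, and then with a rise of about 2 to 4% in detectable differences. The correction is worth making because it costs little and removes any doubt about whether late 1-year visits will be completed and analysed.

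**What to change.** In D.19, restate follow-up as about 20 months from last enrolment and final analysis as about 4 months: 12 + 24 + 20 + 4 = 60. Reconcile the 1-year date with the 13-month date in Section E.1; about 20 months accommodates either at the nominal dates. State that database lock for the 1-year outcomes waits for the last 1-year visit.

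The cost is two fewer months of dedicated analysis and writing time, softened by the plan's statement that analysis is ongoing. Study length and sample size do not change.

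Closing recruitment at month 22 is not a useful alternative. At the planned rate it forgoes 2 × 13.875 = 27.75, or about 28 enrollees. After scaling by 264/333, that is about 22 women at 1 year, roughly as many as it would protect, and their pregnancy and delivery data would be lost as well.

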To ensure retention and to control for contact time, the Comparison Health & Wellness arm receives mailed materials and telephone booster calls on the same schedule as the Lifestyle Intervention arm (Figure 1). In this way, we control for contact time, while keeping the content of the two interventions distinct. These booklets represent high-quality, standard, low-cost, self-help material currently available to the public which focus on non-exercise and non-dietary topics in both English and Spanish. These include the ACOG series of informational booklets on general issues related to health and wellness during pregnancy (e.g., Alcohol and Drug Use during Pregnancy, Easing Back Pain) and the American Academy of Pediatrics booklets on parent resources (e.g., Parenting your Infant). Hispanic control-arm participants in our prior studies (R01DK074876, R01NR011295, R21NR009864) reported that these materials were of interest¹⁴⁹ and differential dropout did not occur between study arms.

D.12. Outcome Variables

D.12.1. Biomarkers of Insulin Resistance and Other CVD Risk Factors

Fasting samples will be collected at a Baystate Reference Laboratory at baseline (~10 weeks gestation), 24-28 wks, and 32-34 wks gestation during routine prenatal care visits, and at 6 wks, 6 mos, and 1 yr, and among children at ~1 yr postpartum (coordinated with timing of the routine lead/CBC screen) (termed “blood draw”). Samples will be stored at -80 degrees Celsius in a freezer at Baystate with temperature monitoring, alarm and a back-up power system. Samples will be shipped periodically to the assaying lab. Residual blood samples will be stored at [name] lab to resolve potential data validation questions related to this study, and will be destroyed 7 years after study completion, unless the participant agrees to storage for future studies (included as “opt-in” in the informed consent form). Quality control for specimen handling will be performed monthly by the head lab technician. Samples will be assayed by [name] (Department of Laboratory Medicine, Harvard University) at Children’s Hospital, Boston, MA.

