
D.12.2. Child Anthropometric Measures

Child anthropometric measures will be obtained within 24 hrs of delivery, 6 wks, 6 mos, and 1 yr postpartum and include measured weight on a calibrated scale, length using a measuring board, and subscapular (SS) and triceps (TR) skinfold thicknesses. We will calculate fetal growth as birth-weight-for-gestational-age z-score and ponderal index (PI) as birth weight (g) x 100/birth length (cm)³. Ponderal index in neonates is closely correlated with estimates of total body fat and thus may indirectly reflect neonatal adiposity.¹⁶¹ We will evaluate change from 0 to 6 mos and from 0 to 12 mos in weight-for-length z score (WFL-z), weight-for-age z score (WFA-z), and length-for-age z score (LFA-z). We will calculate age- and sex-specific scores using U.S.

national reference data (National Center for Health Statistics, CDC Growth Charts). We will use the sum of skinfolds (SS+TR) to estimate overall adiposity, and the ratio of skinfolds (SS/TR) to estimate central adiposity. These anthropometric factors correlate strongly ($r=0.84$) with estimates using total body electrical conductivity.¹⁶² We will measure waist and head circumference. Every 6 mos the staff will be retrained in the anthropometric measurements.

D.12.3. Maternal Information, Delivery Information

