Specific Aim #4: Evaluate the impact of a Lifestyle Intervention on the outcomes of offspring. We will evaluate the impact of intervention arm on the offspring outcomes using the methods described for Aim #1-3. We will also examine GWG and prenatal glycemic factors as predictors of glycemia and weight gain in early infancy and childhood. Important covariates are listed in the covariate section. In models focused on offspring weight gain as the outcome, we will additionally adjust for fetal growth (i.e., BW/GA z score).

Specific Aim #5: Evaluate the cost-effectiveness of the Lifestyle Intervention. We will use procedures developed in our prior studies examining the cost-effectiveness of our interventions.¹⁷¹⁻¹⁷³ We will calculate the ratio of average dollars spent per average incremental improvement in outcome (i.e., GWG, postpartum weight retention, and biomarkers of insulin resistance and CVD risk). Incremental improvement will be defined as the mean change score from baseline for each group, adjusted for baseline values of the outcome measure and other participant characteristics.

Accounting for Missing Data: Although every effort is made to avoid missing data, we plan to use propensity score techniques¹⁷⁴⁻¹⁷⁶ to evaluate the potential sensitivity of results to missing at random assumptions. Multiple comparisons will be addressed by carefully considering the biologic rationale of observed associations.

D.17. Power

To achieve power to detect clinically significant differences requires 300 participants (150 in each intervention arm) at the time of delivery. Based on observed rates in our 2 trials (R01DK074876 and

ASPH/CDC S3948), we conservatively expect 10% of women to leave the New England area, deliver elsewhere, or withdraw during pregnancy, and therefore will recruit 333 women over the 24 mos recruitment period. For offspring outcomes, we calculate that 4% will be excluded for very early preterm birth (<34 wks), miscarriage, or stillbirth resulting in 288 children at delivery. Over the following 1 yr, we conservatively project that an additional 8% of women will be lost to follow-up due to withdrawal or movement out of the New England area. Women who become pregnant again will be censored. Therefore, we expect 264 women and children at 1 yr postpartum.

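### The plan takes a mother who conceives again out of the study and nowhere says that her index child's later Aim 4 follow-up continues

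*Combined protocol and SAP*

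**What the plan says.** The rule for a new pregnancy appears in two forms.

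- E.1, Sources of Materials, removes the woman from the study as a whole: "Women who are identified as having a positive pregnancy test will be removed from the study at the time of their positive pregnancy test".
- D2, repeated in E.1 under Human Subjects Involvement, uses a different term: "Women who become pregnant again in the year following delivery will be censored at the time of their positive pregnancy test". D3 and D.17 also speak of censoring.

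Pregnancy is looked for after randomisation. Randomisation is at about 12 weeks' gestation (D.5), and E.1 says: "A urine pregnancy test will also be performed at the postpartum assessments". E.1 places those assessments at 6 weeks, about 6.5 months and about 13 months.

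The child has its own measurement schedule in D.12.2: "Child anthropometric measures will be obtained within 24 hrs of delivery, 6 wks, 6 mos, and 1 yr postpartum". D.12.1 adds a child blood sample at about 1 year, timed to a routine screen. Table 4 lists seven 1-year child outcomes, each with a projected sample size of 264.

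The paragraph in D.17 that leads to this number starts from offspring outcomes, applies a loss rate for women, and ends: "Women who become pregnant again will be censored. Therefore, we expect 264 women and children at 1 yr postpartum". D.16 analyses Aim 4 by the methods of Aims 1–3, which it describes as intent to treat. No section says what happens to the index child when the mother conceives again.

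**The concern.** A new pregnancy is a sound reason to stop using the mother's weight and biomarkers. It does nothing to the validity of the index child's weight, length, skinfolds, waist circumference, leptin or adiponectin. Yet E.1 takes the woman out of the whole study, not only out of the maternal outcomes, and D.17 lets maternal losses set the child sample size. Staff who follow the text have no stated basis for scheduling the child's remaining visits.

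Two things are at stake. The first is precision for the later child outcomes, lost without need. The second is the randomised comparison: loss of the child would depend on an event after randomisation. Repeat pregnancy could be related to postpartum weight, which the intervention targets, or to breastfeeding, which D.12.4 lists as a covariate.

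**Working it through.** **Inputs from the documents.** D.17: 300 participants at delivery in two equal arms, 4% excluded for very early preterm birth, miscarriage or stillbirth, 8% of women lost over the following year, two-sided alpha of 5%, 80% power. Table 4: N = 264 and the SDs for the 1-year child outcomes.

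**Assumed input.** The share of mothers removed before the 1-year child visit, taken as 5% to 20%. The documents give no repeat-pregnancy rate.

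**Step 1: reproduce the 264.** 300 × 0.96 = 288, and 288 × 0.92 = 264.96, against 264 stated. The 8% loss alone gives the figure. Nothing is subtracted for repeat pregnancy, although the censoring sentence stands directly before it. The number therefore cannot show whether children are kept or lost.

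**Step 2: reproduce Table 4.** Detectable difference = (1.960 + 0.842) × SD × √(4/N). With N = 264 this is 2.802 × 0.1231 = 0.345 SD; the noncentral t gives 0.346 SD. Then:

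- adiponectin: 0.345 × 5.8 = 2.00 (printed 2)
- sum of skinfolds: 0.345 × 4.2 = 1.45 (printed 1.5)
- waist circumference: 0.345 × 2 = 0.69 (printed 0.7)

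The method matches the plan's.

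**Step 3: let each child leave with its mother.** N becomes 264 × (1 − rate). Power at the planned difference is Φ(2.802 × √(N/264) − 1.960).

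| Assumed share removed before the 1-year child visit | Child N | Detectable difference, normal formula (SD) | Detectable difference, noncentral t (SD) | Power at 0.345 SD |
|---|---|---|---|---|
| 0% | 264 | 0.345 | 0.346 | 80.0% |
| 5% | 251 | 0.354 | 0.355 | 78.0% |
| 10% | 238 | 0.364 | 0.365 | 75.7% |
| 15% | 224 | 0.374 | 0.376 | 73.3% |
| 20% | 211 | 0.386 | 0.387 | 70.7% |

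**Step 4: which visits are exposed.** Under scheduled testing, a positive test at 6 weeks puts the 6-month and 1-year child visits at risk. One at about 6.5 months puts only the 1-year visit at risk. One first found at about 13 months need cost no 1-year child data, because child and mother are assessed at about the same time. So if 10% of mothers conceived within the year and half were found only at the last visit, the 5% row would apply. The table also ignores overlap between repeat pregnancy and the 8% already lost. Read against a total repeat-pregnancy rate, each row is therefore an upper bound.

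**The case against.** The best reply is that nothing in the plan removes the child. Every sentence on repeat pregnancy has the woman as its subject. The child schedule in D.12.2 carries no condition on the mother's status, the 1-year blood sample follows the child's own routine screen, and D.4 allows the 6-month and 1-year assessments outside the hospital. Aim 4 inherits an intent-to-treat description. The sponsor may have meant to keep these children all along.

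Much of this stands, and it rules out three stronger readings that a reader might infer:

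- *The child is expressly withdrawn with the mother.* No sentence says so. It is an inference from study-level removal, the joint count of women and children, and silence.
- *Valid child data are thrown away.* Nothing deletes data already collected, and censoring at the time of the test implies that earlier data are kept. At most, later visits are not made.
- *The joint figure of 264 shows children leaving through censoring.* Step 1 shows that no such subtraction was made. The figure fits equally well with every child being kept.

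The reply does not supply the missing instruction. Removal from the study is wider than censoring of maternal outcomes, the two terms are not reconciled, and the only text that connects the rule to child numbers treats mother and child as a pair.

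**Conclusion.** The point holds as a gap in the plan. Followed as written, the index child's later Aim 4 visits may not be collected, because of a post-randomisation maternal event that leaves child outcomes valid. The size is modest: at assumed removal of 5% to 20% before the 1-year child visit, about 13 to 53 fewer children and a loss of about 2 to 9 percentage points of power. This rests on an assumed rate, on every affected child leaving with the mother, and on no overlap with the 8% loss.

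A reader might go further and conclude that the remaining children are no longer a fair randomised comparison. The documents do not support that as a finding. It would need the children actually to be lost, and repeat pregnancy to be related to arm or to child outcome, and no figures are given on either. Bias is possible, but its size and direction are unknown. The gap is still worth closing, because the loss is avoidable and the remedy is the same whichever way the sponsor meant the rule.

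**What to change.** Leave the rule on the mother's own participation unchanged, but reconcile removal (E.1, Sources of Materials) with censoring (D2, D3, D.17 and the earlier part of E.1), so that it is clear what each term covers.

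Then add one statement to D2, D.17 and E.1: *after a positive maternal pregnancy test the index child, with the mother's continued consent, remains in follow-up for the scheduled 6-month and 1-year anthropometry and the 1-year blood draw, and is analysed in its randomised arm.* It should also say that a child due at the same visit as the positive test is measured. With this in place, the 264 for 1-year child outcomes needs no deduction for repeat pregnancy.

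The cost is a short protocol amendment with any matching consent wording. The child measurements are already scheduled. The small downside is that a woman with no further measures of her own is asked to bring the child to at most two visits.
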